#### 7.4 Randomisation

Young people will be randomised in 1:1 ratio to either BA, psychoeducation and TAU or psychoeducation and TAU using stratified block randomisation. Randomisation will be implemented using a web-based system designed and developed by the data management team at York Trials Unit (YTU). The allocation sequence will be generated by a YTU statistician and embedded into the randomisation system. Randomisation will be stratified by site and use randomly-varying blocks of randomly-varying sizes. The Trial Managers based at YTU will inform the behavioural activation therapists who has been allocated to receive behavioural activation.

#### 7.5 Post Randomisation

#### 7.5.1 Blinding

All research assistants collecting follow up data will be blind to participant group allocation. To minimise instances of unblinding, RAs will NOT be informed of, or involved in group allocation, organising therapy sessions, collecting end of treatment questionnaires, completing SAE forms, or access allocation information in the study's database. These duties will be the responsibility of the Trial Managers, with additional support from the qualitative researcher as required, who does not need to be blind to treatment allocation. The RAs will remind each participant at the beginning of their follow-up meetings not to tell the RA about their treatment or who they saw as part of their involvement in the BAY project. Clinical teams will also be trained on the importance of minimising blinding.

If unblinding occurs all blind breaks including accidental unblinding will be recorded by the trial manager and reviewed by the Chief Investigator for patterns in unblindings and be reported to the TSC and DMEC. If unblinding occurs and if feasible an RA from another site will collect follow up data from the young person and carer (if applicable).

#### 7.5.2 Withdrawal of consent

The right to refuse participation without giving reasons will be accepted. Participants are free to withdraw consent and leave the trial at any time without giving reasons and without affecting their care. If a patient withdraws consent to participate, clarification will be sought on whether withdrawal is from the intervention (BA), completing the questionnaires, or both. Data collected up to the date of withdrawal of consent will be used in the analyses.

#### 7.5.3 Treatment discontinuation

In line with usual clinical care, cessation or alteration of trial treatment at any time will be at the discretion of treating clinicians or the participant themselves who may choose to withdraw from the study intervention at any time.

A clinician may decide that a participant should be withdrawn from the research trial if there is reason to believe that they have, after screening and consent, become unsuitable for the study such that the study could become harmful or interfere with other necessary treatments. Reasons for withdrawal could include:

- Very high prolonged risk such as active suicidal behaviours/plans and imminent intent;
- Indication that the intervention is leading to a clear worsening of mental health;
- Further or emergent physical or mental health problems that may exclude the possibility of engagement in the intervention;
- Loss of the capacity to consent to participate in the trial;
- Significant issues with addiction to alcohol or drugs;

If any of these situations for withdrawal occur, the clinician identifying the issue will follow their usual practice within their Trust and notify the PI at the recruiting site.

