# 9.2 Statistical Analysis

Analyses will be conducted in Stata version 17 (or later) following intention-to-treat principles and will follow a detailed pre-specified statistical analysis plan. Statistical

significance will be assessed at the 5% level unless otherwise stated, and 95% confidence intervals will be provided as appropriate. Analyses and results will be reported according to CONSORT guidelines. The flow of individuals through the trial will be reported in a CONSORT diagram, including the number screened (and reasons for ineligibility) and approached for consent (and reasons for non-consent), the number randomised, adherence to allocated treatment, follow-up data completeness and the number of participants included in the primary analysis. Descriptive summaries of continuous data by trial arm will be given in terms of the mean and standard deviation (or median and inter quartile range as appropriate). Descriptive summaries of categorical data will be given in terms of frequencies and proportions. No formal statistical testing will be conducted at baseline. Information on intervention delivery including number and duration of sessions will be summarised descriptively.

The primary outcome (total MFQ-C score) will be summarised descriptively at each time point and analysed using a mixed-effects linear regression model, including all available time points. The model will include trial arm, time, arm-by-time interaction, baseline MFQ score and other important baseline variables as fixed effects. Random effects will be included to account for the repeated measures within patients and for possible clustering by therapist (nested within treatment arm). The primary analysis will compare the groups at 6-months post-randomisation. Secondary analyses will compare the groups at 12-weeks and 12-months post-randomisation. Different covariance patterns for the repeated measurements will be explored and the most appropriate pattern will be used for the final model. Data will be assumed missing at random. Secondary outcomes will be analysed using similar models as described above (with binary outcomes being analysed using a mixed-effects logistic regression model), adjusting for the same fixed and random effects.

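### Clinician-led withdrawal from the trial (7.5.3) does not say that outcome follow-up continues, so 6-month MFQ-C can be lost for reasons related to outcome, possibly unequally between arms

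*Protocol*

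**What the plan says.** Section 7.5.3 (Treatment discontinuation) uses two different terms in adjacent paragraphs. The first concerns stopping treatment and refers to the participant, "who may choose to withdraw from the study intervention at any time". The second says "A clinician may decide that a participant should be withdrawn from the research trial" when the study has become unsuitable for that person. It gives five example reasons:

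- sustained high suicidal risk
- worsening, worded as "Indication that the intervention is leading to a clear worsening of mental health"
- new health problems, physical or mental, that rule out taking part in BA (the text again refers to the intervention)
- loss of capacity to consent
- serious alcohol or drug addiction

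The only stated consequence is that the clinician follows usual Trust practice and notifies the site PI. Nothing is said about later assessments.

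Section 7.5.2 (Withdrawal of consent) is more careful. When a participant withdraws, "clarification will be sought on whether withdrawal is from the intervention (BA), completing the questionnaires, or both". On the use of earlier data, the same section adds: "Data collected up to the date of withdrawal of consent will be used in the analyses". Neither sentence is carried over to clinician-led withdrawal.

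Section 9.2 commits to analysis "following intention-to-treat principles". The primary model is a mixed-effects regression on MFQ-C at all available time points, with baseline MFQ as a covariate and data assumed missing at random. It also plans sensitivity analyses for departures from that assumption.

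**The concern.** The heading of 7.5.3 is about treatment, but the consequence in its second paragraph is about the trial. A site that follows the wording could reasonably stop the 12-week and 6-month assessments for a young person whose only problem, from the trial's point of view, is that BA had to stop.

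The reasons for such a withdrawal are close to the primary outcome. Suicidal behaviour and marked worsening both bear directly on a self-rated depression score. Section 7.5.2 identifies the intervention with BA, so the two reasons that mention the intervention can be invoked mainly in the BA arm. If outcomes are lost this way, and more often in BA, the 6-month comparison loses poor outcomes from one side. The CACE analysis in 9.2 also needs outcomes from BA participants who stopped treatment.

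Whether outcomes are collected after withdrawal is a rule of conduct. A statistical analysis plan cannot repair it later.

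**Working it through.** **1. The plan's own allowance for loss (9.1).** Inputs: 13 groups of 12 in BA, effect size 0.30, baseline correlation 0.45, ICC 0.01 in the BA arm only, 70% retention, 80% power, and 5% significance (two-sided is assumed, as sidedness is not stated).

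- Analysed per arm: 13 × 12 = 156.
- Variance = (1 − 0.45²) × [(1 + 11 × 0.01)/156 + 1/156] = 0.7975 × 2.11/156 = 0.0108, so SE = 0.104.
- Power: 82.3% by the normal approximation, or 80.5% with a t reference on about 41 degrees of freedom, against 80% stated.
- Recruitment: 312/0.70 = 445.7, giving 446.

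The figure is reproduced. It implies that 446 × 0.30 = 133.8, about 134 participants, have no 6-month value. The allowance covers loss for any reason, so clinician-led withdrawals fall inside the 134 and are not an addition to it.

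**2. The two withdrawal rules side by side.**

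| | Withdrawal of consent (7.5.2) | Clinician-led withdrawal (7.5.3) |
|---|---|---|
| What is left | BA, questionnaires, or both: clarified | The research trial |
| Data already collected | Used | Not stated |
| Later MFQ-C | Follows from the clarification | Not stated |

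**3. The five reasons by arm.** Two (worsening attributed to the intervention, problems preventing engagement in it) refer to the intervention. Three (high risk, lost capacity, addiction) can arise in either arm.

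**4. What the primary model sees.**

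- If follow-up stops before 12 weeks, the participant has no post-baseline MFQ-C. Baseline is a covariate, so nothing in the outcome data reflects the worsening.
- If it stops after 12 weeks, the 12-week score is used. Missing at random is reasonable if the worsening already shows at 12 weeks, and doubtful if it came later.

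**5. Size.** Let w be the share of an arm lost through clinician-led withdrawal. Let D be how many MFQ-C points worse their unseen 6-month scores are than the model predicts, taken as equal in both arms. The model understates each arm's mean by w × D, so the bias in BA minus control is −(w_BA − w_control) × D. A negative value favours BA. Neither w nor D is in the documents. For illustration only, with assumed D from 5 to 15 points:

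| w_control | w_BA | Bias, D = 5 to 15 | Share of the 5-point target |
|---|---|---|---|
| 5% | 5% | 0 | 0% |
| 2% | 5% | −0.15 to −0.45 | 3% to 9% |
| 0% | 5% | −0.25 to −0.75 | 5% to 15% |
| 2% | 10% | −0.40 to −1.20 | 8% to 24% |
| 0% | 10% | −0.50 to −1.50 | 10% to 30% |

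If the rates were reversed (5% control, 2% BA), the sign would flip to +0.15 to +0.45. The table shows how the bias behaves; it is not an estimate.

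**The case against.** The strongest reply is that 7.5.3 is silent rather than wrong. It sits under a heading about treatment and nowhere says that questionnaires stop. That is correct, and it limits the point. A reader might infer that the protocol orders the worst outcomes to be discarded. It does not: loss of follow-up is the natural reading of being withdrawn from the trial, not a stated rule.

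Three other stronger readings are tempting and are not supported.

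- *That intention-to-treat is breached.* Missing outcomes neither move nor exclude anyone according to treatment received. What is strained is the missing-at-random assumption.
- *That the bias certainly favours BA.* Imbalance towards BA is plausible, both from the two intervention-linked reasons and because each BA session checks symptoms and risk (8.1.1). But usual care may mean waiting with nothing delivered (8.2), so high-risk withdrawals could be commoner among controls.
- *That safety monitoring of the most unwell ends.* Section 7.6 has serious events reported by clinical teams, therapists and site teams. Participants remain under CAMHS unless discharged, and records are screened (7.3, 8.2). Nothing says that these stop. Only the route through follow-up questionnaires would be lost.

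It is also fair to say that 9.2 plans sensitivity analyses for departures from missing at random, and that the model uses the 12-week score. Both soften the problem. Neither supplies an outcome that was never collected.

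Finally, some trial withdrawals are proper. Where capacity is lost or the research itself may harm, a clinician needs to be able to stop research contact, and any change must preserve that.

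**Conclusion.** The point stands as a gap with a consequence. Sections 7.5.2, 7.5.3 and 9.2 do not fit together on whether follow-up continues after a clinician-led withdrawal. As worded, 7.5.3 permits avoidable loss of 12-week and 6-month MFQ-C for reasons tied to outcome. The loss may be greater in the BA arm and could then favour BA.

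The documents do not allow the size to be estimated. It is zero if withdrawals are balanced in number and severity, and it grows with the difference in rates and with how much worse the unseen scores are than predicted. The conclusion rests on reading withdrawal from the trial as ending assessments. It applies mainly to the risk, worsening and engagement reasons. The planned sample size is unaffected. With about 134 of 446 already expected to lack a 6-month value, preventable outcome-related loss is worth removing by amendment.

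**What to change.** Leave the clinical criteria in 7.5.3 unchanged and settle only what happens to data collection.

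- Apply the distinction in 7.5.2 (intervention, questionnaires, or both) to clinician-led decisions in both arms.
- State that a decision to stop BA does not by itself end follow-up. MFQ-C at the scheduled time points (including 12 months where due), records-based data and serious adverse event reporting continue by default.
- List the exceptions: consent to these is withdrawn by the young person, or by the carer where carer consent applies (7.2 does not require it at 16 to 17); capacity to consent is lost; or the clinician judges that the research contact itself should stop.
- State that data collected before a clinician-led withdrawal are used, as for withdrawal of consent.
- Record the reason, date and scope of each withdrawal, and report them by arm. Table 1 already lists a trial-withdrawals form.

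The cost is one paragraph in an amendment and a line in site guidance. The downside is a few more follow-up contacts with unwell participants, on whose timing the clinical team can advise.

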#### 7.5.4 End of Trial

The end of trial is defined by the last visit and completion of data collection of the last participant undergoing the trial. The sponsor, or delegated individual in the study team must notify the NIHR and HRA of the end of a clinical trial within 90 days of its completion.

# 7.6 Monitoring and reporting Adverse Events (AE) and Serious Adverse Events (SAE)

Table 3: Definitions of AE and SAE

Term	Definition
Adverse Event (AE)	
 
An adverse event is;
 
any unintentional, unfavourable clinical sign or symptom
 
any new illness or disease or the deterioration of existing disease or illness
 

Serious Adverse Event (SAE)	A serious adverse event is any untoward medical occurrence that:  (a) results in death (b) is life-threatening (c) requires inpatient hospitalisation or prolongation of existing hospitalisation (d) results in persistent or significant disability/incapacity (e) consists of a congenital anomaly or birth defect (f) is otherwise considered medically significant by the investigator  Other 'important medical events' may also be considered serious if they jeopardise the participant or require an intervention to prevent one of the above consequences.

	NOTE: The term "life-threatening" in the definition of "serious" refers to an event in which the participant was at risk of death at the time of the event; it does not refer to an event which hypothetically might have caused death if it were more severe.
Related Unexpected Serious Adverse Event (RUSAE)	
 
The National Research Ethics Service (NRES) defines related and unexpected SAEs as follows:
 
'Related' – that is, it resulted from administration of any research procedures; and
 
'Unexpected' – that is, the type of event is not listed in the protocol as an expected occurrence.
 

Due to the population that will be recruited into the trial, some events including mood fluctuations and self-harm not requiring medical intervention will be common and expected and therefore we will not be monitoring this as an adverse event. Due to the difficulties of defining these types of events for the purposes of the study, we will focus on serious adverse events. As participants will be under the care of CAMHS throughout the trial (unless discharged due to improvements), emotional and behavioural events will be monitored and the young person will receive appropriate care through CAMHS following their usual procedures. The research team will therefore monitor only serious adverse events as outlined below:

- Requires hospitalisation for mental health reasons (or prolongation of existing hospitalisation), including any A&E attendance.
- Results in a clinical decision being made that a participant's mental state has seriously deteriorated.
- Results in persistent or significant disability or incapacity.
- Results in death.
- Is otherwise considered medically significant (including a mental act assessment).

Clinical teams will be trained to report the serious adverse events outlined above to the Trial Managers from the York Trials Unit. Clinical professionals will be asked to complete a serious adverse events form and send it to the Trial Managers, who will process it at the trials unit.

Items relating to hospitalisation on the CA-SUS as well as concerning responses on the self-harm and suicidality questions will be flagged up at all follow-up timepoints in both arms and the Trial Manager will be made aware as soon as possible and liaise with the clinical team from that participants site. A designated person from the research team will schedule a phone call with the participant and/or their carer and discuss the adverse event. The TM or designated person from the research team will record it using a serious adverse events form. Copies of any serious adverse forms will be sent to the site and clinical teams will be informed.

If a serious adverse event is disclosed to a research assistant or BAY therapist, or the site team become aware of such an event in the TAU arm, it will be reported to the Trial Manager as soon as possible and the same above process will occur.

The Chief Investigator will review any serious adverse events if they arise. Any serious adverse events will be reported to the study sponsor within 3 working days of being notified.

Safety issues will be reported to the REC in the annual progress report. A summary of all events will also be reported to the TSC and Sponsor.

Expedited reporting of events to the REC and the Sponsor will be subject to current NRES guidance, the YTU Standard Operating Procedures (SOPs) and Sponsor requirements.

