Consent	Paper/Online Consent Form/REDCap	Self-completion / Research Assistant		X							
Demographics	CRF	Self-completion/ RA assistance if requested		X							

Strengths & Difficulties	Questionnaire	Self-completion/RA								
Questionnaire (SDQ)-		assistance if requested		X	X	X	X			
Parent version		·								
Development and Well- Being Assessment	Online	RA led alongside		X						
(DAWBA)		participant if requested								
Mood and Feelings		Self-completion/RA								
Questionnaire (MFQ)  Parent version	Questionnaire	assistance if requested		Х	X	X	X			
Carer EQ-5D-5L	Questionnaire	Self-completion/RA assistance if requested		Х		X				
Generalised Anxiety Disorder (GAD-7)	Questionnaire	Self-completion/RA assistance if requested		х		Х				
Patient Health Questionnaire (PHQ-9)	Questionnaire	Self-completion/ RA assistance if requested		х		X				
Optional Qualitative Interview	Semi-structured interview	Interview				Х				
		R	ESEARCH ASSISTANT/I	RESEARCH TEAM						
						(X – IF				
Treatment as Usual	Questionnaire	Self-completion/Clinical				PARTICIPANT IS				
Questionnaire		records				NOT DUE A 12	X			
Questionnane		records				MONTH FOLLOW-				
						UP)				
Safety Reporting	CRF	Research								
		Assistant/PI/Clinician								
BA Completion (Discharge Information)	CRF	Clinician/Research Team			X (collected throughout)					
Trial withdrawals	CRF	Research Assistant/PI/Clinician	X (collected throughout)							

Table 2: Summary of BAY therapist assessments.

Assessment	Source	Method of Completion										
			Pre- trial	1 st session	2 nd session	3 rd Session	4 th Session	5 th Session	6 th Session	7 th Session	8 th Session	End of trial
			delivery	Session	30331011	Session	Session	30331011	30331011	30331011	30331011	triai
BAY THERAPIST												
Demographics	CRF	Therapist	Х									
BA Session Log	Questionnaire	Therapist		X	X	X	X	X	X	X	X	
Safety Reporting	CRF	Therapist	X (collected throughout)									
End of BA treatment Questionnaire	Questionnaire	Therapist									X (after final session)	
Fidelity to BA Checklist*	CRF	Independent Assessor										Х
Qualitative Interview	Semi- structured interview	RA led										х

\* Random selection of recordings based on pre-selection criteria: commence in year 2 of trial

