#### 8. INTERVENTION AND COMPARATOR

#### 8.1. Intervention: Blended Behavioural Activation

#### 8.1.1 Content

"Be Active" (13) workbooks (8 sessions) have been developed to include blended delivery plus TAU+psychoeducation versus TAU+psychoeducation. The BA program is designed to be structured, yet flexible in delivery. Each BA workbook consists of an overview of the session, agenda, symptom and risk check, homework review, session content, session summary (feedback and goals review) and carer information. The first 4 sessions focus on introducing BA, goals, values, and activity scheduling (See Table 4)

The BAY BA training programme has 3 components: a clinician's manual which includes guidance on providing remote delivery, cultural adaptation, and links to demonstration videos; training to use workbooks including understanding of fidelity ratings, cultural issues, and remote delivery (initial 2 days training plus 2 further days led by local therapy leads which will include practice case discussion); and required reading of existing material on behavioural activation and depression (RCPsych/minded.org).

A website for blended delivery will be developed in order to enhance our current basic website in order to improve the experience of remote therapy, and will include animations. Young people fed back that our original website was easy to use, but would benefit from more functionality and improved design. Therefore, in the first phase of the study, we will co-design an enhanced platform with YP, focussing on making the site more engaging, usable, safe and accessible. The platform will comply with NHS Digital-recommendations, and will not be a Medical Device. We will use Agile methodology and track analytics to understand how the platform supports intended outcomes (Yardley et al, 2016). Development will include 4 co-design workshops with YP (n=4) and members of the research and software teams. In month 7, we will beta-test with 5 healthy volunteer YP, 5 professionals, & assess user acceptance in month 8.

**Table 4:** Eight BA modules in BAY

Module	Topics covered
Module 1: Goal setting, Psychoeducation and Recording	
 
Engagement, personalisation, getting to know the young people and establishing a therapeutic rapport
 
Setting out rationale and contents of the programme
 
Finding person-centred ways to plan and record activities
 

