# 8.2 COMPARATOR: Psychoeducation plus Treatment as Usual

Following randomisation, all young people will receive a website link to a psychoeducation leaflet from the Royal College of Psychiatrists. The leaflet provides information about depression and signposting to where young people can find extra support. Carers (if involved) will also receive carer information regarding depression in young people, as well as signposting for carers.

Usual practice in CAMHS can vary widely (experience of the trial team and in national reports eg CQC 2018). Treatment as usual may be no intervention whilst on an internal CAMHS pathway waiting list; signposting to alternative sources of support; risk and case management; referral to a psychiatrist for medication review; or referral for psychological therapy, however, these generally have long waiting lists. Currently waiting lists for therapy in CAMHS services vary and can be months.

We will record and monitor what treatment as usual means for each young person recruited into the study. We will devise a pro-forma for RAs to complete using clinical records. This will capture all interventions that were delivered in CAMHS, including BA, and recording of risk issues such as attendance at A&E.

When reviewing clinical records we will particularly look for any aspects of treatment as usual that are similar to BA e.g. rating and structuring activities. Even in sites where BA-type interventions may be included in treatment as usual (such as brief psychosocial support), from experience within the associated teams, it is expected that these interventions are sufficiently different to our BA. For example, they are not standardised or do not include key components such as activity scoring.

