# Monitoring Contamination

- Training: Therapists and supervisors will be informed at the BA initial training event about the importance of avoiding contamination in the TAU arm post randomisation. BAY leads will then disseminate information to clinics and managers and regularly remind them of this.
- At sites: BA therapists will avoid delivering regular sessions to young people allocated to treatment as usual alone post randomisation, in conjunction with managers/site leads.
- Aspects of care questionnaire: All YP to complete an 'aspects of care questionnaire' which asks about BA elements of their treatment from any source at follow up (including external to CAMHS).

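### Serious adverse events are ascertained more intensively in the BA arm than in the TAU arm, and section 7.6 does not use the record review that could narrow the gap

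*Protocol*

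**What the plan says.** Section 7.6 of the protocol limits safety monitoring to SAEs and sets out how they reach the trial.

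- Routes open in both arms: "Clinical teams will be trained to report the serious adverse events outlined above to the Trial Managers from the York Trials Unit". In addition, hospitalisation items on the service-use schedule and concerning self-harm or suicidality answers "will be flagged up at all follow-up timepoints in both arms". Research assistants (RAs), who see both arms, pass on anything disclosed to them. Table 1 in section 3.3 has a safety reporting row that is not restricted by arm.
- Route in the BA arm only: the BAY therapist. Section 8.1.1 says "Each BA workbook consists of an overview of the session, agenda, symptom and risk check", and there are eight workbooks. "Table 2: Summary of BAY therapist assessments" (section 3.3) has the therapist completing safety reporting throughout. Under Monitoring Contamination in section 8.4, "BA therapists will avoid delivering regular sessions to young people allocated to treatment as usual alone post randomisation", so this route is kept out of the control arm on purpose.
- The TAU counterpart, in the same sentence of 7.6 as the therapist: an event is reported if "disclosed to a research assistant or BAY therapist, or the site team become aware of such an event in the TAU arm".

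Section 8.2 describes the control condition as variable: "Treatment as usual may be no intervention whilst on an internal CAMHS pathway waiting list" is one possibility, with signposting, risk and case management, psychiatric referral and psychological therapy as others.

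Separately, sections 7.3 and 8.2 provide for a review of clinical records for each participant at the end of participation. It captures the CAMHS interventions delivered, "including BA, and recording of risk issues such as attendance at A&E". Section 7.6 counts any A&E attendance for mental health reasons as an SAE but does not mention this review.

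**The concern.** An SAE enters the count only if someone connected with the trial learns of it. A BA participant has up to eight scheduled meetings with a trial-trained therapist who checks risk and has a safety form to complete. A TAU participant on a waiting list may have no scheduled clinical contact between follow-ups, so an event then surfaces through the site team or at the next questionnaire.

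Two of the SAE criteria in 7.6 depend heavily on contact: a clinical decision that mental state has seriously worsened, and an event judged medically significant. The first cannot be recorded unless a clinician has seen the young person.

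At stake is how SAE counts by arm are read by the steering committee, the sponsor and, eventually, readers of the trial report. More recorded events in BA could reflect closer observation alone, or could mask a real reduction in events.

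**Working it through.** The protocol states no SAE rate, detection rate or safety power, so there is no figure to reproduce. The check compares the sources by arm and then illustrates the possible size.

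**Sources by arm**

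| Source | BA | TAU |
|---|---|---|
| Trained clinical teams (7.6) | yes | yes |
| Service-use and self-harm items at 12 weeks, 6 months and, in a subset, 12 months | yes | yes |
| Disclosure to an RA | yes | yes |
| Therapist with a risk check in each workbook and safety reporting throughout | yes | no |
| Record review at end of participation | done, not linked to SAEs | done, not linked to SAEs |

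The only difference between the columns is the therapist row. The questionnaire row also has a limit. The revised sample size in section 9.1 assumes 70% retention. If that applied to the 6-month visit, about 0.30 × 223 = 67 participants per arm would give no questionnaire data then, and detection for them would rest mainly on clinical contact, which is where the arms differ.

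**Illustration with assumed inputs**

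Let *p* be the true SAE risk, equal in both arms. Let *s* be the share of events found by the common sources, and *t* the share of otherwise missed events that the therapist finds. There are 223 per arm (section 9.1).

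- Observed risk in TAU = *p* × *s*
- Observed risk in BA = *p* × [1 − (1 − *s*)(1 − *t*)]
- Apparent risk ratio = [1 − (1 − *s*)(1 − *t*)] / *s*, which does not depend on *p*

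Worked case, *p* = 0.10, *s* = 0.7, *t* = 0.5:

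- TAU: 223 × 0.10 × 0.7 = 15.6 events
- BA: 1 − 0.3 × 0.5 = 0.85, and 223 × 0.10 × 0.85 = 19.0 events
- Ratio: 0.85 / 0.7 = 1.21

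The table varies *t* from 0.25 to 0.75. The last column is the chance that a two-sided 5% two-proportion test would declare a difference when none exists, over *p* from 5% to 20%.

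| Common-source detection *s* | Apparent risk ratio | False-positive rate |
|---|---|---|
| 0.9 | 1.03 to 1.08 | 5% to 7% |
| 0.7 | 1.11 to 1.32 | 5.5% to 25% |
| 0.5 | 1.25 to 1.75 | 7% to 63% |

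The bias always runs towards more recorded events in BA. It is small where the common sources work well and material where they do not. Setting *t* = 0, meaning that only common sources count, gives a ratio of 1.00 and a 5% error rate. That assumes those sources are equally sensitive in both arms; it does not show that they are.

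**The case against.** The strongest reply is that the control arm is far from unobserved. Clinical teams are trained to report whatever the allocation, the questionnaire flags apply to both arms, and RAs see everyone. Section 7.6 expects participants to remain under CAMHS care unless they are discharged because they have improved. Self-harm and suicidality are also self-reported on the same schedule in both arms, which already gives one symmetric safety comparison. All this stands. It narrows the gap without closing it, and deaths and admissions are probably caught about equally well in both arms.

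A reader might infer that the trial's between-arm safety comparison is biased. The protocol does not support that. Sections 7.6 and 9.2 specify no formal SAE comparison; 7.6 speaks only of reports and summaries to oversight bodies. An analysis may sit in the statistical analysis plan, which is not at hand. The text supports a risk of bias of unknown size.

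A reader might also infer that events known only through a therapist should be left out of the comparison. That would remove genuine SAEs from the treated arm and could understate harm. Nor would it give full symmetry, because BA is delivered by CAMHS staff and the records reviewed cover BA as well.

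Finally, the serious-deterioration criterion is itself a clinical decision, so contact changes how often the event arises as well as how often it is captured. No restriction by source corrects that. Unequal contact is inherent in adding a therapy to usual care.

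**Conclusion.** The point holds as a risk of detection bias. Section 7.6 gives the BA arm a scheduled source of SAE reports that the TAU arm lacks, so SAE counts by arm may show more events in BA with no true difference. The size cannot be established from the protocol. The ratios of 1.03 to 1.75, and the middle case of 1.21, rest entirely on assumed detection rates and equal true risk. The risk is greatest for serious deterioration in mental state, for medically significant events, and among participants not retained.

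This is partly a matter of data collection, so an analysis plan alone cannot repair it: control events that no source captured with a date cannot be recovered later. The one clear omission is that a review of every participant's records already picks up A&E attendance, a listed SAE, and 7.6 makes no use of it.

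**What to change.** In section 7.6:

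1. State that the record-review pro-forma will capture, with dates and in both arms, the listed SAE criteria that records can verify: A&E attendance, admission, Mental Health Act assessment and death.
2. State that Trial Managers will reconcile the review with the SAE log and complete any missing SAE forms. This should not fall to the RAs, whom section 7.5.1 keeps from completing SAE forms to protect blinding.
3. Use the reporter item already on the adverse event form (section 3.3.1) to record every source of each SAE, not only the first.
4. Report all SAEs by arm. Add a table restricted to events captured by sources applied identically in both arms: the record review other than BA therapist notes, and the service-use and self-harm items. Show events known only through a BAY therapist separately, and keep them in the overall count.
5. State that differences in contact-dependent events should be read with the unequal contact in mind.

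Immediate reporting by therapists is unchanged. The cost is a few more lines on a pro-forma already completed for everyone, the reconciliation work and one extra table. The asymmetry in contact-dependent events is not fully removed.
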